indicates no significant adverse effect on clinical functional status (NYHA class, walk distance, cardiac output, pulmonary artery pressure, pulse, blood pressure). Thus, we propose to determine whether treatment with a β -blocker reverses biochemical abnormalities in PAH that lead to maladaptive right ventricular remodeling and failure, utilizing a blinded, placebo-controlled, randomized trial of carvedilol in PAH patients for six months. We will also evaluate clinical parameters of cardiovascular function in relation to changes in the biochemical effects of treatment. Because PAH patients ultimately die of heart failure, carvedilol was chosen as the β -blocker in this study, as it is one of the two β blockers currently FDA-indicated for the treatment of heart failure, and has been extensively well-studied for use in very severe heart failure. Carvedilol blocks $\beta 1AR$ and $\beta 2AR$, as well as $\alpha 1AR$, the latter blocks vasoconstriction and may benefit for PAH patients by decreasing afterload. Additionally, carvedilol is inexpensive and generally well-tolerated; specifically, during long term treatment, intolerance to drug in patients with severe heart failure (class III-IV) did not differ from patients with mild-to-moderate heart failure (class II).

Specific Aims and Hypothesis

We hypothesize that use of carvedilol in patients with PAH will reverse loss of, and resensitize β -adrenoreceptors, increase production of NO, and reduce activation of HIF-1 α , which altogether will improve right and left ventricular function, decrease right and left ventricular size, and improve exercise and functional capacity. To test this, we propose a blinded, placebo-controlled, randomized trial of carvedilol at a fixed low-dose or dose-escalating pattern of therapy in PAH patients for six months with a one-week open-label run-in phase.

A. Primary Aim

To determine whether treatment with carvedilol reverses biochemical abnormalities associated with PAH, we will assess the following:

- Activation of HIF-1 α (co-primary end points):** We will assess activation of HIF-1 α via measurement of plasma erythropoietin and myocardial glucose uptake during fasting gated FDG-PET. We already know that erythropoietin is elevated in PAH and that FDG-uptake is high. We expect both to decrease on drug.

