- NO synthesis:** We will determine if carvedilol restores eNOS activity and NO synthesis by measuring the global arginine bioavailability ratio (GABR), exhaled NO, and circulating nitrogen oxides (plasma nitrite, nitrate and urinary nitrate). We will use GABR, exhaled NO and plasma nitrite and urinary nitrate to monitor responses to our strategy for restoration of NO synthesis. We expect GABR and all measures of nitrogen oxides to increase with Carvedilol, just as in LV failure treated with β -blockers.
- β AR recovery:** We will assess β AR numbers and activation by measurement of levels of β AR on the surface of cells, and the intracellular messenger cAMP via flow cytometric analysis of circulating mononuclear cells before, during, and after treatment with Carvedilol. We will also use circulating mononuclear cells to determine phospho- β AR levels. These novel tests were innovated by our group for this study. We anticipate that receptor numbers and cAMP will increase, while phospho- β AR levels will decrease in the circulating mononuclear cells of patients on drug.

B. Secondary Aim

To determine whether reversal of the biochemical abnormalities as above correlate with an improvement in clinical parameters of disease severity, including right ventricular function, heart chamber size, exercise and functional capacity, and quality of life, we will assess the following:

- Ventricular function and structure:** We will utilize echocardiogram to evaluate cardiac chamber size and function, including estimation of RV systolic pressure (RVSP) and measurement of RV fractional area change (RVFAC), RV ejection fraction, myocardial performance index (MPI) of the RV, tricuspid annular plane systolic excursion (TAPSE), tissue Doppler-derived systolic velocity of the lateral tricuspid annulus (S' velocity), three-dimensional RV ejection fraction, and longitudinal strain and strain rate with tissue Doppler techniques. Because dynamic physiologic insights into RV function will be valuable, we will capitalize on the ability to obtain radionuclide ventriculography measure of RV ejection fraction using the

cardiac-gated FDG. Although software packages are available for measurement of LV ejection fraction by PET, they do not allow for corresponding RV measurements, and new software is needed for this task. We plan to develop software for calculation of RV ejection fraction by the FDG-PET, and it will be available for the clinical trial.

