We will enroll 68 subjects with pulmonary arterial hypertension Class 1,3,4 and 5 (Nice 2013) with symptoms consistent with NYHA Class I-III.

Inclusion criteria

- Men and women age 18 or older not greater than age 65 years
- Diagnosis of pulmonary arterial hypertension class 1,3,4 and 5 (Nice 2013)
- NYHA/WHO Class I-III
- PAH medications must have been initiated according to the latest consensus statement recommendations and remained stable for the last 30 days
- Women of child-bearing age must use a double-barrier local contraception till completion of the study

- Subjects must demonstrate understanding of the study, sign the informed consent, and have a reliable method of communication for contact and ability to comply with the study requirements.

Exclusion criteria

- Participation in any other treatment studies during enrollment
- Significant illness in the past 30 days requiring hospitalization
- Hepatic insufficiency (transaminase levels >4 fold the upper limit of normal or bilirubin >2 fold the upper limit of normal),
- History of HIV, Hepatitis B or C
- Serum creatinine >2.8 mg/dl
- Pregnancy, breast-feeding, or lack of safe contraception
- Acute decompensated heart failure within past 30 days
- Known allergy or intolerance to carvedilol or other β blockers
- Significant, persistent bradycardia (resting heart rate <50 bpm) or hypotension (systolic blood pressure <100 mmHg or mean blood pressure <70 mmHg) at the time of enrollment
- Second or third-degree AV block without pacemaker
- Use of hypotensive drugs that deplete catecholamines (such as reserpine and monoamine oxidase inhibitors) which may lead to greater signs of hypotension or bradycardia
- Use of amiodarone, diltiazem, verapamil, clonidine
- Active bronchospasm
- Other medical and psychosocial conditions as determined by principal investigator deemed unsuitable for enrollment

C. Sample Size Rationale and Estimate

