Final eligibility will be determined by the investigator after review of the medical record and data gathered during the screening visit. Eligible, enrolled subjects will undergo additional baseline procedures:

- Quality of life questionnaires
- Fasting Gated FDG-PET scan
- Echocardiography
- Blood draw for flow cytometry, plasma nitrite and nitrate, global arginine bioavailability ratio (GABR), Erythropoietin, & NT-proBNP
- Urine for nitrate
- Exhaled NO

E. Intervention

Open-label Run-in Phase

All enrolled, eligible subjects will receive an open-label carvedilol therapy at starting dose of 3.125 mg twice daily for one week and be monitored at the Clinical Research Unit for the first-dose challenge of Carvedilol. Upon discharge, enough carvedilol to complete the 1-week run-in period will be dispensed by a licensed provider. Subjects will be instructed to return in 1 week with any

unused medication. Those individuals who are eligible for randomization to the trial will undergo the procedures summarized in Table A1 “Run-in Week”.

Double-blinded Randomized Phase

At the end of the 1-week run-in phase, subjects who have tolerated the low-dose carvedilol without severe or limiting side effects, still meet the inclusion and exclusion criteria, and who wish to continue in the study will be randomized to one of three arms: placebo, low-dose carvedilol, or escalating dose carvedilol for 6 months. Subjects and the investigators will be blinded to their group assignment for the duration of the study.

- Group 1 will receive a placebo drug to take twice daily for 6 months.
- Group 2 will receive carvedilol at a dose of 3.125 mg twice a day for 6 months.
- Group 3 will receive carvedilol in a dose escalation scheme. They will be given 3.125 mg tablets to take bid for 1 week, followed by 6.25 mg bid for 1 week, followed by 12.5 mg bid for 1 week with the option to increase to the max dose of 25 mg bid for the remainder of the study. During up titration, if a dose is not tolerated, the dose will be decreased to the previous tolerated dose for the remainder of the study.

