For measurement of laboratory parameters, blood will be drawn from a peripheral vein. Complete blood cell count (CBC), metabolic panel, and NT-proBNP, will be measured using standard laboratory techniques. The remaining laboratory parameters will be measured by the investigators in the laboratory. Erythropoietin (mIU/mL) will be measured via enzyme-linked immunosorbent assay (ELISA). The proportion of cells positive for cAMP will be determined via flow cytometry. Circulating mononuclear cells will also be assessed for phospho-βAR content by immunoprecipitation and western blot, to evaluate resensitization of the receptor. Plasma nitrite and nitrate will be measured, and fasting levels of arginine, ornithine, and citrate in order to calculate the GABR [Arg /(Orn + Cit)].

Urine collection

A urine specimen will be obtained in a sterile urine specimen cup for use of measuring urine nitrate and for pregnancy testing of women who are peri- or premenopausal.

NYHA/WHO Functional Classification

The patient will be classified into class I-IV based on a subjective assessment of their symptomatology and limitation of physical activity, as described below:

- Class I: No limitation of physical activity. Ordinary physical activity does not cause dyspnea or fatigue, chest pain, or near syncope.
- Class II: Slight limitation of physical activity. They are comfortable at rest. Ordinary physical activity causes undue dyspnea or fatigue, chest pain or near syncope.
- Class III: Marked limitation of physical activity. They are comfortable at rest. Less than ordinary activity causes undue dyspnea or fatigue, chest pain or near syncope.
- Class IV: Inability to carry out any physical activity without symptoms. These patients manifest signs of right heart failure. Dyspnea and/or fatigue may even be present at rest. Discomfort is increased by any physical activity.

Six Minute Walk Test

The six-minute walk test is a simple means of assessing functional capacity utilizing a 100-foot hallway¹. The distance that a patient can walk as quickly as possible on a flat, hard surface in six minutes will be measured in meters & feet. The test will be done according to American Thoracic Society recommended guidelines.

Echocardiogram

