Doppler echocardiography will be performed by a single well-experienced echo technologist ([name]) for all studies to estimate PAP, RV and LV function using previously validated methods. Right ventricular function will be assessed via measurement of RV fractional area change (RVFAC), RV ejection fraction, myocardial performance index (MPI) of the RV, tricuspid annular plane systolic excursion (TAPSE), tissue Doppler-derived systolic velocity of the lateral tricuspid annulus (S' velocity), three-dimensional RV ejection fraction, and longitudinal strain and strain rate with tissue Doppler techniques (conventional technique, 2-dimensional speckle tracking and velocity vector imaging). Among these methods, the most used parameters are RVFAC, TAPSE, S' velocity of the lateral tricuspid annulus, and RV MPI.

Exhaled NO measurement

The participant will take in a deep breath and exhale through a mouthpiece attached to the nitric oxide analyzer (Aerocrine). This will be repeated for a total of three exhaled NO readings. NO is measured using the American Thoracic Society recommended guidelines.

FDG-PET scan

Cardiac-gated fasting FDG-PET scans will be conducted on fasting patients at baseline and 6 months. Finger stick blood sugar will be measured to assure fasting state (blood sugar < 120 mg/dl). Patient data will be acquired using a clinical PET/CT scanner (Biograph mCT 128) having time-of-flight capable PET detectors. First, a low-dose CT scan will be acquired to provide an attenuation map for PET data corrections. Then, a PET scan will be acquired in list mode for fifteen minutes with ECG signals obtained during the scan. Both static and gated images will be reconstructed using advanced iterative algorithms available on the scanner. All subjects will be fasting 8 h prior to and during the study, then injected with 370 MBq (10 mCi) FDG and scan performed at 1.5 h post-injection. Images will be analyzed in a blinded fashion by [name] using an image fusion workstation (MSViewer, CPS Innovations, Knoxville, TN) with region-of-interest (ROI) measuring tools. A total of five ROI will be measured in heart (left & right atria, RV, LV and IVS). In addition, ROI will be measured for the blood pool of the thoracic aorta. FDG uptake depends on factors including time between injection and scan, blood glucose, and body mass. For consistency, relative uptake will be normalized to blood pool FDG in thoracic aorta.

Safety and tolerability outcomes

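### The only definition of GABR names citrate where citrulline is needed, and urine nitrate has no stated correction for dilution

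*Combined protocol and SAP*

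**What the plan says.** The Blood draws text in G. Data Collection requires "fasting levels of arginine, ornithine, and citrate in order to calculate the GABR [Arg /(Orn + Cit", where the bracket closes. No other section gives the formula or lists its components, and citrulline is not mentioned anywhere in the document.

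For urine, the Urine collection text says "A urine specimen will be obtained in a sterile urine specimen cup for use of measuring urine nitrate"; the same specimen serves for pregnancy testing. The baseline procedures in D. Enrollment list only "Urine for nitrate". Table 1 schedules urinary nitrate at baseline, the run-in week, month 1, and months 3 and 6. None of these places gives a unit, a timed collection, a urine volume, a urine creatinine or an osmolality.

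Under A. Primary Aim, NO synthesis, the purpose and expected direction are stated: "We will use GABR, exhaled NO and plasma nitrite and urinary nitrate to monitor responses to our strategy for restoration of NO synthesis" and "We expect GABR and all measures of nitrogen oxides to increase with Carvedilol". The label "co-primary end points" is attached only to the HIF-1α measures (erythropoietin and FDG uptake).

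**The concern.** GABR is meant to set arginine against the products it is turned into. Citrate belongs to energy metabolism. With citrate in the denominator, one of the two arginine products is left out and an unrelated quantity takes its place. Citrate and citrulline can both be measured, and both shorten to Cit, so the formula does not expose the error and a laboratory could follow the text literally. A rise or fall in such a ratio could then be reported as a change in arginine availability when it was not one.

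For urine nitrate, the concentration in a single specimen depends on how dilute the urine is as well as on how much nitrate is excreted. The protocol deals with a comparable problem for FDG, where "relative uptake will be normalized to blood pool FDG in thoracic aorta", but states nothing similar for urine. What is at stake is precision in a measure used to judge whether NO synthesis has been restored.

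**Working it through.** **1. GABR.** The plan gives no numerical value for this ratio, so the check is of the definition. Write A for arginine, O for ornithine and X for the third analyte.

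- As written: GABR = A/(O + X), with X = citrate.
- From basic biochemistry (not stated in the protocol): arginase takes arginine to ornithine; NO synthase takes arginine to citrulline plus NO. The analyte that pairs with ornithine is therefore citrulline.
- The analysis plan compares changes from baseline. On the log scale the change is Δln A − Δln(O + X). A small relative change in X moves ln GABR by −X/(O + X) times that change. With X = citrate, this part of the change says nothing about arginine use, and the citrulline part is missing.

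The documents give no plasma levels, so X/(O + X) cannot be calculated and no size is claimed here.

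**2. Urine nitrate: what the text contains.** Every mention was compared: Primary Aim, the baseline list, Table 1 and Urine collection. None states a correction. The only creatinine named as such is a serum exclusion limit, "Serum creatinine >2.8 mg/dl", which does not correct a urine concentration. That the value is a spot one is an inference from the cup specimen; the protocol does not use the term.

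**3. Urine nitrate: what dilution could cost.** The plan gives no variability for nitrate, so this borrows the FDG inputs from C. Sample Size Rationale and Estimate: coefficient of variation (CV) 50%, a two-fold difference in medians, 14 per group and α = 0.025. Two-sided testing is assumed, since sidedness is not stated.

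- SD of the log ratio = √ln(1 + 0.5²) = 0.472; difference = ln 2 = 0.693.
- Reproducing the plan's own figure first: the noncentral t gives 92.6% power at n = 14, and 90% is reached at n = 13. If 0.5 is used directly as the log SD, power at n = 14 is 89.4%. The stated 14 per group for 90% power is therefore consistent with the plan's inputs.
- Add dilution with assumed CV c at each visit, independent between visits. The variance of the log 6-month/baseline ratio becomes 0.472² + 2 ln(1 + c²). For c = 30% this is 0.223 + 0.172 = 0.395, so SD = 0.629.

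| Assumed dilution CV per visit | SD of log ratio | Power, n = 14 per group | n per group for 90% power |
|---|---|---|---|
| 0% | 0.472 | 0.926 | 13 |
| 20% | 0.549 | 0.825 | 17 |
| 30% | 0.629 | 0.703 | 22 |
| 40% | 0.721 | 0.571 | 29 |
| 50% | 0.818 | 0.457 | 36 |

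The table assumes that 0.472 contains no dilution noise. If it already contained some, the loss would be smaller. It also overstates what a creatinine ratio could recover if that ratio removes only part of the noise.

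**The case against.** The strongest reply is that the first point is a naming slip and the second an unreported detail. The name of the ratio and the abbreviation Cit both point to citrulline. The assay is run by the investigators' own laboratory, the group that chose the ratio, which makes it less likely that citrate is really being measured. A laboratory manual may specify how urine nitrate is reported. Exhaled NO and plasma nitrite and nitrate also address NO synthesis, so that question does not rest on these two markers. All of this stands, and it limits the point to correcting an assay definition and adding a normalisation. It does not remove the need, because the protocol's only definition of GABR remains wrong as written.

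A reader might infer more, in three ways that the documents do not support:

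- *That citrate would move with treatment and mimic an NO effect.* The reversal of the glycolytic switch described in the background was seen in cultured endothelial cells. Nothing in the plan predicts a change in plasma citrate, and the inference also presumes that citrate is what is assayed.
- *That carvedilol biases urine nitrate through the kidney.* Renal insufficiency appears only in a general list of less common side effects. Nothing shows that the drug changes urine concentration. In a randomised, blinded comparison, dilution unrelated to treatment adds noise to the group difference and does not bias it.
- *That urine nitrate is defined as an uncorrected value.* The protocol is silent on how it is reported, which is not the same thing.

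**Conclusion.** The GABR definition should be corrected: as written it names an analyte that is not an arginine product, in the one place where the ratio is defined. Whether any measurement is affected cannot be settled from the documents. The urine point is secondary. The missing correction costs precision by an amount the plan does not allow one to estimate; the illustrative fall in power from 93% to between 82% and 46%, for dilution CVs of 20% to 50%, rests wholly on borrowed and assumed inputs.

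It would go too far to say that the two measures do not track NO synthesis. Urine nitrate still carries signal when uncorrected. GABR with citrulline would itself be a measure of substrate availability and not of NO synthesis directly, since the citrulline that NO synthase produces sits in its denominator. Both are mechanistic measures under the primary aim. Erythropoietin, FDG uptake and the sample size calculation are untouched.

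**What to change.** 1. Confirm with the laboratory which analyte is measured, then replace citrate with citrulline in Blood draws, so that GABR = arginine/(ornithine + citrulline). Describe it as a measure of arginine availability. If citrulline is already measured, this costs one word. If citrate has been measured, citrulline would have to be assayed; the documents do not say whether plasma is kept for that.
2. In Urine collection, define the endpoint as nitrate divided by creatinine in the same specimen, state the unit, and apply it at every Table 1 visit with urinary nitrate. That is five occasions per participant (baseline, run-in, months 1, 3 and 6), so at most 5 × 68 = 340 inexpensive assays on urine already collected, with no added visit or sample. The ratio relies on creatinine excretion being reasonably stable within a patient. A timed collection would also deal with dilution, at more burden to participants.

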If any patients in any arm of the study appear intolerant of drug (based on symptoms such as persistent light-headedness, sitting systolic BP<85 mm Hg or resting pulse<50, or hospitalization for heart failure), they will be provided a new bottle of pills labeled “week-dose reduction” as following: subjects on dose-escalating carvedilol will be provided a new bottle of carvedilol at the prior week's dose, subjects on fixed low-dose of carvedilol will be provided placebo pills, subjects on placebo will be provided a new placebo pill bottle. Once dose reduction has occurred in the dose-escalating arm, subjects will be maintained on that set dose throughout the remainder of the study, with no further escalation of dose. If signs or symptoms of subjects in any arm persist despite the dose reduction, dose reduction will again be implemented as follows: subjects on dose-escalating carvedilol will be provided a new bottle of carvedilol at half the current reduced dose, subjects on fixed low-dose carvedilol will again be provided placebo pills, subjects on placebo will again be provided a new placebo pill bottle. Of note, only 3 total dose reductions will be allowed during the entire 6 month study. Following 3 dose reductions are implemented, if subjects are still intolerant, they will be removed from all study drug.

Subject Instruction

All subjects will be advised to take the study medication with a small meal. All subjects will receive a daily phone call for the first week after start of carvedilol during the run-in. Thereafter, patients will be called weekly to screen for side effects and to monitor their clinical status. Patients will be provided a home blood pressure monitoring device and asked to record pulse and blood pressure in the morning and evening at the same time each day with instructions to call at any time systolic BP<85 mm Hg or pulse<55. Lightheadedness is expected to occur, but in 99.5% of cases in prior studies of severe heart failure, this resolves without problems. Patients will be instructed to sit up and rise slowly. Patients will also be instructed to call if they experience any new or worsening symptoms, or require hospitalization or unscheduled doctor visits.

F. Follow-up Schedule

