Safety monitoring parameters will be collected via daily and/or weekly phone calls and at all follow-up visits. Subjects will be asked whether they have experienced any side effects and to describe these symptoms and to provide the BP and heart rate home records, which will be recorded in the electronic medical record. We will also monitor subjects throughout their enrollment and record whether there have been any deaths or hospitalizations during the study.

Compliance

Subjects will be asked to bring the study medication and bottles with them to each follow-up visit. A tablet count will be performed to estimate compliance. Subjects will also be asked how many tablets per day they have been taking on average, and how many times a week they miss a dose.

H. Early Withdrawal

Patients may be withdrawn from the study for any of the following reasons:

- Pregnancy
- Lung transplantation
- Unacceptable side effects or toxicity, as deemed by the principal investigator
- Patient non-adherence or inability to communicate with the patient
- More than three dose reductions of medications required
- Patient request to withdraw from the study

I. Data Monitoring

a. Quality Control

Data will be monitored for quality control by the study coordinator, statistician and principal investigator. Within the study database, conventional limits will be set on each data entry cell to minimize entry of erroneous values.

b. Recruitment

Problems with recruitment will be assessed after 12 months of enrollment of the first patient. If less than a fourth of the sample size has been recruited for the study, additional recruitment strategies will be addressed and implemented.

c. Benefit/Risk and Subject Safety

This study will be submitted to the Institutional Review Board for review of the benefits and risks of the proposed trial. We plan to comprise a Data and Safety Monitoring committee to oversight

the trial. Overall, we believe the potential benefits of carvedilol for PAH outweigh the potential risks of the study.

Potential Benefits

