A potential direct benefit to the subjects includes possible improvement in clinical symptoms for those randomized to carvedilol treatment. This study may also be beneficial for future patients because the results of this investigation will enhance our mechanistic understanding of the pathophysiology of PAH, how β blockers affect patients with pulmonary arterial hypertension, and may therefore lead to the development of new treatments for PAH and heart failure in general.

Potential Risk Associated with Carvedilol Therapy

Common side effects associated include hypotension, dizziness, fatigue, hyperglycemia, diarrhea, weight gain, and weakness. Less common side effects include bradycardia, syncope, peripheral edema, angina, AV block, palpitation, cerebrovascular accident, hypertension, headache, depression, hypercholesterolemia, gout, hyperkalemia, hyponatremia, nausea, vomiting, abdominal pain, weight loss, melena, impotence, anemia, thrombocytopenia, back pain, arthralgia, paresthesia, blurry vision, renal insufficiency, cough, pulmonary edema, and dyspnea. Rare adverse reactions may include anaphylaxis, alopecia, aplastic anemia, asthma, bronchospasm, bundle branch block, cholestatic jaundice, erythema multiforme, exfoliative dermatitis, GI bleed, hearing loss, hyperbilirubinemia, hypokalemia, interstitial pneumonitis, leukopenia, migraine, MI, pancytopenia, rash, seizure, Stevens-Johnson syndrome, toxic epidermal necrolysis, urinary incontinence, and xerostomia. Subjects will be closely monitored for side effects throughout the study period and withdrawn from the study should unacceptable toxicity or side effects develop.

Risk Associated with PET/CT Scans

The radiation associated with the cardiac PET/CT scans is a potential risk to human subjects. For each scan, the injection of ^{18}F -FDG (10 mCi) results in an effective dose equivalent of 7.3 mSv. The CT portion of the study is performed at a very low dose for the purpose of PET data correction and results in an effective dose equivalent of 0.2 mSv. For this study, each subject may be exposed to a total of 14.6 mSv over the course of two PET/CT scans, which is considered to be in the acceptable range for diagnostic imaging studies. For comparison, the typical annual exposure to background radiation (radon, other terrestrial sources, and cosmic rays) is about 3 mSv, which means that the radiation exposure from this study is similar to that of seven years of typical exposure to background sources.

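### Patients withdrawn from the study for side effects, non-adherence or repeated dose reductions are not asked back for the month-6 FDG-PET, so the intent-to-treat comparison of this co-primary may become one of scanned patients

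*Combined protocol and SAP*

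**What the plan says.** Section H begins "Patients may be withdrawn from the study for any of the following reasons". Three of the listed reasons matter here: "Unacceptable side effects or toxicity, as deemed by the principal investigator", "Patient non-adherence or inability to communicate with the patient" and "More than three dose reductions of medications required". The section on carvedilol risks repeats the rule for toxicity without the permissive verb: subjects are to be "withdrawn from the study should unacceptable toxicity or side effects develop".

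Blinded Medication Dispensing (section E) is worded differently. It caps dose reductions at three and then says that "if subjects are still intolerant, they will be removed from all study drug". That ends drug, not participation, and the text does not mention later visits. Before that point, reduced patients stay in the blinded study; for example, "subjects on fixed low-dose of carvedilol will be provided placebo pills".

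The FDG-PET section and Table 1 schedule the scan at baseline and month 6 only. The last column of Table 1 covers months 3 and 6 or study exit, but its FDG-PET entry is restricted to month 6. Section F schedules nothing after the exit visit. Erythropoietin, the other co-primary, is drawn at month 3 and at month 6 or exit.

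Section E (Double-blinded Randomized Phase) and the Analysis Plan both promise an intent-to-treat comparison of the three arms. The Analysis Plan names repeated measures ANOVA and t-tests. It gives no method for a missing scan and no sensitivity analysis.

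**The concern.** The FDG-PET endpoint is the ratio of month-6 to baseline uptake. A patient who leaves before month 6 has no ratio, and there is no intermediate PET value for a repeated measures model to use. Assigning that patient to the randomized arm for analysis does not create an outcome.

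Side effects and non-adherence can depend on treatment. If they do, the patients without a scan differ between arms in ways that randomization no longer balances. The result would then describe those who stayed rather than all randomized patients. Data not collected cannot be recovered at analysis, and in arms of about 16 one or two patients matter.

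**Working it through.** **1. The plan's own figure.** Inputs from section C: alpha 0.025 (taken as two-sided, since the plan does not say), power 90%, a 50% lower median ratio, CV of ratios at most 50%, 14 per group.

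- SD of the log-ratio = √ln(1 + 0.5²) = 0.472; effect = ln 0.5 = −0.693.
- Noncentral t: 13 per group are needed, and power at 14 is 92.6%. With SD taken as 0.50, 15 are needed and power at 14 is 89.4%. The stated 14 is reproduced.
- Dropout of 10%: 14/0.9 = 15.6, so 16 per arm and 48 in all. Run-in loss of 30%: 48/0.7 = 68.6, against 68 stated.

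The sample size therefore already expects about 14 scanned of 16 randomized per arm. This assumes equal allocation, which the plan does not state.

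**2. Who can be lost.**

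| Situation | Where | Month-6 scan |
|---|---|---|
| Dose reduced, still on blinded capsules | Section E | Scheduled; stays in assigned arm |
| Off all drug after three reductions | Section E | General schedule appears to apply; not stated |
| More than three reductions needed | Section H | May be withdrawn from the study; no return stated |
| Side effects or non-adherence | Section H (toxicity also in the carvedilol risk section) | Study withdrawal; no return stated |

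Rows two and three can describe the same patient, with different consequences for follow-up.

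**3. Effect on the estimate.** Planned loss is 0.10 × 16 = 1.6, so 1 or 2 patients per arm. Suppose completers show a ratio of 0.50 relative to placebo and k of 16 low-dose patients are lost. The all-randomized ratio depends on what is assumed for them:

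| Assumed response of those lost | k = 1 | k = 2 |
|---|---|---|
| Same as completers | 0.50 | 0.50 |
| None: 0.5^((16−k)/16) | 0.52 | 0.55 |
| One SD (0.472) above the placebo mean | 0.54 | 0.58 |

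Last row: k = 1, exp[(15 × −0.693 + 0.472)/16] = exp(−0.620) = 0.54; k = 2, exp[(14 × −0.693 + 2 × 0.472)/16] = exp(−0.547) = 0.58.

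**4. Power if they are kept** (16 randomized per arm, SD 0.472, two-sided 0.025; retained cases by simulation of 200,000 trials).

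- Completers only, symmetric loss: 94.4% (15 v 15), 92.6% (14 v 14).
- All 16 per arm scanned, 1 or 2 low-dose patients without response: about 92% or 86%.
- Two retained with half the log effect: about 93%. Two retained who respond equally: about 96%.

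**The case against.** The case against has several sound parts.

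- **Off drug is not out of the study.** Section E removes intolerant patients from drug only, the month-6 schedule has no on-drug condition, and section E keeps patients in their arm whatever happens to dose. This stands. A reader might infer that everyone taken off drug loses the scan, and the documents do not support that. What remains is that section H allows the same intolerance to end participation.
- **Withdrawal is optional and blinded.** Section H says only that patients may be withdrawn, and its criteria apply to all arms. This stands against any claim that the comparison will become one of completers. Blinding does not prevent loss caused by the drug's side effects.
- **Table 1 may provide an exit scan.** The month-6 restriction may mean only that no scan is done at month 3. This is unresolved, but an early scan would not be the 6-month value.
- **Dropout is already allowed for.** Adding patients protects power. It does not address which patients are lost.
- **The powered comparison is the least exposed.** Everyone randomized had tolerated the low dose in the run-in, and a low-dose patient who is reduced receives placebo. Tolerance-related loss is more plausible in the escalation arm, probably through withdrawal before the three reductions are used up. Loss through non-adherence remains possible in any arm.
- **Some loss cannot be recovered.** Non-adherence shares an entry with inability to reach the patient, and withdrawal at the patient's request is listed separately. How many of the planned 10% could be scanned is unknown.

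**Conclusion.** The point holds in a limited form. Sections H and I (carvedilol risks) allow randomized patients to leave the study for reasons that may depend on treatment. Nothing secures their only post-baseline FDG-PET scan, and no rule covers its absence. The intent-to-treat promise may therefore not be met for this co-primary. Erythropoietin is partly protected by its month-3 and exit draws.

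At the documented dropout rate the shift is modest: from 0.50 to 0.52–0.55 with no response among those lost, or to about 0.54–0.58 if they worsen by one SD. These figures rest on 16 per arm, CV 50%, loss falling in the carvedilol arm, and assumed responses that the documents do not supply.

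Two stronger readings are not supported. One is that the bias favours carvedilol: neither its direction nor its presence can be established from the text. The other is a shift to 0.57–0.62, which needs 20–30% loss with no response at all (0.5^0.8 = 0.57; 0.5^0.7 = 0.62), well above the planned 10%. This is a worthwhile and inexpensive improvement, not a flaw that invalidates the design.

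**What to change.** Leave every criterion for stopping drug as it is. Reconcile section H, Blinded Medication Dispensing and the carvedilol risk paragraph so that they state:

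1. Stopping or reducing study drug, or non-adherence, does not by itself end follow-up.
2. Unless they withdraw consent, cannot be contacted or cannot be scanned, such patients attend the scheduled month-3 and month-6 assessments, including the month-6 FDG-PET, and are analysed in their randomized arm.
3. Whether Table 1 provides an exit scan. If it does, that scan does not replace the 6-month ratio in the primary analysis, and the text should say how it fits the radiation estimate, which is given "over the course of two PET/CT scans".

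In the Analysis Plan, add a report of missing scans by arm and a sensitivity analysis that varies the missing log-ratios in every arm, placebo included, with some values worse than the placebo mean. It should not be called a bound: stopping at no response gives 0.55 for two patients lost, whereas a one-SD worsening gives 0.58.

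**Cost.** Amendment wording, including a change to a safety statement, and some retention effort. The scan is already planned for every subject. The effect may be diluted: power of about 92% or 86% with one or two retained non-responders, against 94.4% or 92.6% for completers with symmetric loss. In the worse case that is about 6 points, the price of estimating the effect that the plan promises. If retained patients respond like the others, power is slightly higher than with completers alone.
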